**4.1.1.3. *Safety Follow-Up Period******Visit 801***

All randomized participants are required to complete a safety follow-up visit (Visit 801), according to the SoA. Participants discontinuing the study drug early and performing an ED visit will also be asked to perform the safety follow-up visit (see Section 7.2). During the safety follow-up period, participants will not receive study drug. Participants are also required to return any remaining study diaries to the study site at the end of this period.

Visit 801 (safety follow-up visit) should be performed 4 weeks after the last visit in the treatment period (Visit 28 or Visit 99) or 4 weeks after the ED visit for randomized participants who decline to return for Visit 99.

**4.1.2. *Study Procedures***

Participants will perform study procedures listed in the SoA (Section 1.3).

Study participants will be permitted to use concomitant medications that they require during the study, except certain excluded medications (see Section 5.2) that may interfere with the assessment of efficacy and safety characteristics of the study treatments.

Study governance considerations are described in detail in Section 10.1 (Appendix 1).

## 4.2. Scientific Rationale for Study Design

Tirzepatide is CCI

It is administered QW by SC injection.

As a dual GIP/GLP-1R agonist, tirzepatide could exceed the efficacy of selective GLP-1R analogs by recruiting metabolically active tissues not targeted by selective GLP-1R analogs (for example, adipose tissue as indicated by the observation of increased energy utilization) (Müller 2018) and has the potential to reach higher efficacy in target tissues, such as insulin-producing pancreatic beta-cells that express both GIPR and GLP-1R, before reaching its therapeutic limitation. Results from a Phase 2 study (GPGB) demonstrated that tirzepatide use in participants with T2DM was associated with a substantial, dose-dependent weight loss, greater than the weight change observed with dulaglutide, a specific GLP-1R agonist. General safety characteristics of all studied doses of tirzepatide were similar to that of the GLP-1R agonist class, consisting mainly of nausea, vomiting, and diarrhea. In general, these events were transient and mild or moderate in severity, with few severe episodes. These data suggest that tirzepatide has the potential to be a pharmacologic treatment for chronic weight management.

Although GI AEs were more common in the 15-mg arm of tirzepatide in the Phase 2 study (GPGB), this dose demonstrated the highest efficacy in terms of weight loss. An optimized dose escalation regimen proposed in the current Phase 3 Study (GPHM) to improve tolerability (and supported by a dose-escalation algorithm from study GPGF and PK/PD modelling) should enable a use of the 15-mg dose to maximize effects on body weight.

Study GPHM is designed to determine the impact of treatment with tirzepatide MTD (10 mg or 15 mg QW) compared with placebo on body weight management after an intensive lifestyle modification program in study participants without T2DM who have obesity or are overweight.

Study GPHM consists of a lead-in period of 12 weeks during which participants will undertake an intensive lifestyle modification program (Heymsfield et al. 2003). Traditionally, guidelines have restricted pharmacotherapy use to those who do not respond to diet and exercise but newer guidelines are recommending the addition of pharmacotherapy in those who lose weight with diet and exercise but may not be able to maintain the weight loss or may require additional weight loss. The goal of the lead-in period, therefore, is to identify participants who initially respond to lifestyle-based therapy so that the benefit of tirzepatide can be evaluated in this population. Only those participants who achieve  $\geq 5.0\%$  weight loss during the intensive lifestyle lead-in period will be randomized.

A low-calorie diet (LCD) was chosen for the lead-in period because it is a discrete, structured and intensive intervention that is recognized as the centerpiece of dietary therapy for overweight and obesity (NHLBI 2000). In those who can adhere to it, an LCD may achieve greater weight loss in the short-term than the moderate 500 kcal/day deficit diet being applied in combination with tirzepatide throughout the obesity Phase 3 program. Moreover, an LCD was chosen over the option of a very low-calorie diet (VLCD) because VLCDs are only used in limited circumstances by specialized practitioners experienced in their use and with special monitoring and supplementation (NHLBI 2000). Because VLCDs are not recommended as routine therapy for overweight or obesity, using a VLCD would have affected the generalizability of the results.

Clinical trials have also shown that LCDs are as effective as VLCDs at 1 year in achieving weight loss (Wadden et al. 1994).

After randomization, participants in both the placebo and MTD tirzepatide arms will continue to receive lifestyle modification counselling consistent with current guidelines for weight management (Jensen et al. 2014; NHLBI 2013). Specifically, participants will consult with a dietician, or equivalent qualified delegate, throughout the post-randomization treatment period to achieve an approximately 500 kcal/day energy deficit through a combination of caloric restriction and increased physical activity (see Section 5.3).

The planned duration of treatment for the primary endpoint at 72 weeks allows for a 52-week treatment period at the dose achieved following dose escalation to either 10 mg or 15 mg. This duration is considered appropriate to assess the full effects and balance of risk and benefit for tirzepatide MTD compared with placebo on body weight and is consistent with regulatory guidelines (FDA 2007; EMA 2016). A placebo comparator was selected for this trial in accordance with regulatory guidance (FDA 2007; EMA 2016).

The effects of drug cessation will be assessed in the 4-week safety follow-up/observational period. To minimize the potential confounding effect of changes to concomitant medications, participants will be permitted to use concomitant medications that do not interfere with the assessment of efficacy and safety characteristics of the study treatments.

### **4.3. Justification for Dose**

Tirzepatide MTD (10 mg or 15 mg QW) will be evaluated in this study. These doses and associated escalation schemes were selected based on assessment of safety, efficacy (weight loss), and GI tolerability data in Phase 1 and 2 studies in patients with T2DM, followed by exposure-response modeling of the data that predicted weight loss in patients with overweight or obesity.

In a 26-week, Phase 2 study (GPGB) of participants with T2DM, tirzepatide reduced body weight by 4.8 kg, 8.7 kg, and 11.3 kg at dose levels of 5, 10, and 15 mg, respectively, whereas the weight loss observed in participants on dulaglutide, a selective GLP-1R agonist, used at the dose of 1.5 mg, was 2.7 kg (Frias et al. 2018).

Similar to the GLP-1R agonist class, most of the tirzepatide AEs were dose-dependent and GI-related, consisting mainly of nausea, vomiting, and diarrhea. In general, these events were mild or moderate in severity, with few severe episodes, and transient.

Tirzepatide doses of 10 mg and 15 mg were selected based principally on the following criteria:

- each dose provides robust weight loss relative to placebo
- the percent of patients achieving  $\geq 10\%$  weight loss is higher with 15 mg than 10 mg, and
- safety and tolerability were supported by Phase 2 results and/or PK/PD modeling.

Dosing algorithms starting at a low dose of 2.5 mg accompanied by dose escalation of 2.5-mg increments every 4 weeks should permit time for development of tolerance to GI events and are predicted to minimize GI tolerability concerns. The maximum proposed dose of 15 mg maintains an exposure multiple of 1.6 to 2.4 to the no-observed adverse effect level doses in 6-month monkey and rat toxicology studies.

#### **4.4. End of Study Definition**

Section 7.2 describes the criteria used to determine if a participant has completed the study.

The end of the study is defined as the date of the last visit of the last participant in the study or last scheduled procedure shown in the SoA for the last participant in the trial globally.

## 5. Study Population

Prospective approval of protocol deviations to recruitment and enrollment criteria, also known as protocol waivers or exemptions, *is not permitted*.

### 5.1. Inclusion Criteria

Participants are eligible to be included in the study only if all of the following criteria apply:

#### Type of Participant and Disease Characteristics

1. Have a BMI of:
  - $\geq 30$  kg/m^2 or
  - $\geq 27$  kg/m^2 and previously diagnosed with at least 1 of the following weight-related comorbidities
    - Hypertension: treated or with systolic blood pressure  $\geq 130$  mmHg or diastolic blood pressure  $\geq 80$  mmHg
    - Dyslipidemia: treated or with low-density lipoprotein (LDL)  $\geq 160$  mg/dL (4.1 mmol/L) or triglycerides  $\geq 150$  mg/dL (1.7 mmol/L), or high-density lipoprotein (HDL)  $< 40$  mg/dL (1.0 mmol/L) for men or HDL  $< 50$  mg/dL (1.3 mmol/L) for women
    - Obstructive sleep apnea
    - Cardiovascular disease (for example, ischemic cardiovascular disease, New York Heart Association [NYHA] Functional Classification Class I-III heart failure)
2. Have a history of at least 1 self-reported unsuccessful dietary effort to lose body weight
3. In the investigator's opinion, are well-motivated, capable, and willing to:
  - learn how to self-inject study drug, as required for this protocol (visually impaired persons who are not able to perform the injections must have the assistance of a sighted individual trained to inject the study drug; persons with physical limitations who are not able to perform the injections must have the assistance of an individual trained to inject the study drug)
  - inject study drug (or receive an injection from a trained individual if visually impaired or with physical limitations)
  - follow study procedures for the duration of the study, including, but not limited to following lifestyle advice (for example, dietary restrictions, exercise plan), maintaining a study diary, and completing required questionnaires

#### Participant Characteristics

4. Are at least 18 years of age and age of majority per local laws and regulations
  - a. Male participants:

- Male participants with partners of childbearing potential should be willing to use reliable contraceptive methods throughout the study and for 5 half-lives of study drug plus 90 days, corresponding to 4 months after the last injection.
- b. Female participants:
  - Female participants not of childbearing potential may participate and include those who are:
    - infertile due to surgical sterilization (hysterectomy, bilateral oophorectomy, or tubal ligation) or congenital anomaly (such as Mullerian agenesis) or
    - Post-menopausal – defined as either:
      - A woman at least 40 years of age with an intact uterus, not on hormone therapy, who has cessation of menses for at least 1 year without an alternative medical cause, AND a follicle-stimulating hormone (FSH)  $\geq 40$  mIU/mL; women in this category must test negative in pregnancy test prior to study entry
      - or**
      - A woman 55 or older not on hormone therapy, who has had at least 12 months of spontaneous amenorrhea
      - or**
      - A woman at least 55 years of age with a diagnosis of menopause prior to starting hormone replacement therapy
  - Female participants of child-bearing potential (not surgically sterilized and between menarche and 1-year postmenopausal) must:
    - test negative for pregnancy at Visit 1 based on a serum pregnancy test
    - if sexually active, agree to use 2 forms of effective contraception, where at least 1 form is highly effective for the duration of the trial plus 30 days, corresponding to 2 months after the last injection, and
    - not be breastfeeding

**Note:** Contraceptive use by men or women should be consistent with local regulations regarding the methods of contraception for those participating in clinical studies.

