Allowable Deviation (days)		±3	±3	±3	±3	±3	±3	±3	±3	±3	±3	±3	±3	±3	±3	±3	±3	±3	±3	±3	±3	±3	±3	±3	±3	±3	±3	±7	±7		±3
Fasting Visit	X	X		X		X		X		X	X	X	X	X	X	X			X			X			X			X	X	X	X
Telephone Visit			X		X		X		X								X	X		X	X		X	X		X	X				
Lifestyle Program Instruction only			X		X		X		X																						
Chemistry panel (includes Cr for eGFR calculation and glucose)	X									X			X			X				X			X			X			X	X	X
	The CKD-EPI equation will be used by the central lab to estimate and report eGFR.																														
Insulin	X									X			X			X			X			X			X			X		X	X
C-peptide	X									X			X			X			X			X			X			X		X	X
Lipid panel	X									X						X													X	X	X
Free fatty acids	X									X						X												X	X	X	
Serum pregnancy	X									X																					
	For women of childbearing potential only.																														
Urine pregnancy (local)										X			X			X			X			X			X			X		X	
	A urine pregnancy test must be performed at Visit 10 with the result available prior to first injection of study drug(s) for women of childbearing potential only. Additional pregnancy tests (beyond those required by the SoA) should be performed at any time during the trial if a menstrual period is missed, there is clinical suspicion of pregnancy, or as required by local law or regulation.																														
Follicle-stimulating hormone test	X																														
	Follicle-stimulating hormone test is to be performed at Visit 1 for postmenopausal women at least 40 years of age with an intact uterus, not on hormone therapy, and who have had spontaneous amenorrhea for more than 1 year without an alternative medical cause.																														
Calcitonin	X									X			X			X												X		X	X
Pancreatic amylase	X									X			X			X												X		X	X
Lipase	X									X			X			X												X		X	X
Urinary albumin/creatinine ratio	X									X						X												X		X	X
Cystatin-c	X									X						X												X		X	X

Visit	1	2	3	4	5	6	7	8	9	10	11	12	13	14	15	16	17	18	19	20	21	22	23	24	25	26	27	28	99	ED	801		
Week of Treatment	-14	-12	-11	-10	-9	-8	-6	-4	-2	0	4	8	12	16	20	24	28	32	36	40	44	48	52	56	60	64	68	72	72		4 wks Post TxP		
Allowable Deviation (days)		±3	±3	±3	±3	±3	±3	±3	±3	±3	±3	±3	±3	±3	±3	±3	±3	±3	±3	±3	±3	±3	±3	±3	±3	±3	±3	±7	±7		±3		
Fasting Visit	X	X		X		X		X		X	X	X	X	X	X	X			X			X			X			X	X	X	X		
Telephone Visit			X		X		X		X								X	X		X	X		X	X		X	X						

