## 10.5. Appendix 5: Contraceptive Guidance and Collection of Pregnancy Information

### Definitions:

#### Woman of Childbearing Potential (WOCBP)

A woman is considered fertile following menarche and until becoming post-menopausal unless permanently sterile (see below).

If fertility is unclear (for example, amenorrhea in adolescents or athletes) and a menstrual cycle cannot be confirmed before first dose of study intervention, additional evaluation should be considered.

Women in the following categories are not considered women of childbearing potential

Article I. Premenarchal

Article II. Premenopausal female with 1 of the following:

- Documented hysterectomy
- Documented bilateral salpingectomy
- Documented bilateral oophorectomy

For individuals with permanent infertility due to an alternate medical cause other than the above, (for example, Mullerian agenesis, androgen insensitivity), investigator discretion should be applied to determining study entry.

**Note:** Determination can come from the site personnel's review of the participant's medical records, medical examination, or medical history interview.

Article III. Postmenopausal female

- A postmenopausal state is defined as either
  - A woman at least 40 years of age with an intact uterus, not on hormone therapy, who has cessation of menses for at least 1 year without an alternative medical cause, AND an FSH  $\geq$ 40 mIU/mL; or
  - A woman 55 or older not on hormone therapy, who has had at least 12 months of spontaneous amenorrhea; or
  - A woman at least 55 years of age with a diagnosis of menopause prior to starting hormone replacement therapy (HRT).
- Females on HRT and whose menopausal status is in doubt will be required to use one of the nonestrogen hormonal highly effective contraception methods if they wish to continue their HRT during the study. Otherwise, they must discontinue HRT to allow confirmation of postmenopausal status before study enrollment.

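### Criterion 4b and Appendix 5 classify a premenopausal woman with tubal ligation alone differently, so her scheduled urine pregnancy tests number either 0 or 7

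*Protocol*

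**What the plan says.** **Section 5.1, criterion 4b.** Female participants not of childbearing potential include those "infertile due to surgical sterilization (hysterectomy, bilateral oophorectomy, or tubal ligation") or a congenital anomaly, and those who are post-menopausal. Women of childbearing potential are then described as "not surgically sterilized and between menarche and 1-year postmenopausal". They must have a negative serum pregnancy test at Visit 1 and, if sexually active, use two forms of contraception.

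**Section 10.5, Appendix 5.** The definition headed Woman of Childbearing Potential starts from the opposite default: "A woman is considered fertile following menarche and until becoming post-menopausal unless permanently sterile (see below"). The exempt group "Premenopausal female with 1 of the following" has three entries: documented hysterectomy, documented bilateral oophorectomy and "Documented bilateral salpingectomy". Tubal ligation is not among them. For permanent infertility from another medical cause, "investigator discretion should be applied to determining study entry".

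**Section 1.3, SoA.** The Visit 10 urine test is required "with the result available prior to first injection of study drug(s) for women of childbearing potential only". The same row is marked at Visits 13, 16, 19, 22, 25 and 28 and at early discontinuation. The note adds: "Additional pregnancy tests (beyond those required by the SoA) should be performed at any time during the trial if a menstrual period is missed", on clinical suspicion, or where local law requires it.

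**Section 10.2, Appendix 2.** For the screening pregnancy criteria, the reader is sent to Section 5.1. There is no corresponding reference for Visit 10 or later tests.

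**The concern.** The SoA uses childbearing potential as the switch for routine pregnancy testing, and the protocol defines that term in two ways that disagree for one group of women. Two sites following the protocol in good faith could treat identical women differently. One would test before the first injection and every 12 weeks afterwards, and the other would schedule no test at all.

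What is at stake is a safety check before exposure to an investigational drug. The protocol acts on the result: Section 7.1 lists onset of pregnancy among the reasons for stopping study drug, and Section 7.2 withdraws a participant who becomes pregnant. Following criterion 4b as written means that a woman whom Appendix 5 presumes fertile has no routine test to trigger either step.

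**Working it through.** No statistical formula applies. The check sets the texts side by side and then counts the scheduled tests.

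**Step 1. Classify a premenopausal woman whose only sterilization is tubal ligation.**

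| Text | Rule | Result |
|---|---|---|
| Criterion 4b | Ligation is named as surgical sterilization; childbearing potential requires not being surgically sterilized | Not of childbearing potential |
| Appendix 5 | Presumed fertile unless permanently sterile as listed; ligation is not listed | Of childbearing potential |

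**Step 2. Look for text that says which definition governs.**
- Appendix 2 sends only the screening criteria to Section 5.1, so Visit 1 is settled.
- The Appendix 5 discretion clause gives Mullerian agenesis and androgen insensitivity as examples. Even if it were stretched to cover ligation, it concerns study entry and not scheduled testing.
- The SoA urine row cites neither section.

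Nothing therefore settles Visit 10 or the later tests.

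**Step 3. Count the urine tests in the SoA row.**
- Pre-dose: Visit 10 (Week 0) = 1.
- Treatment period: Visits 13, 16, 19, 22, 25 and 28 = Weeks 12, 24, 36, 48, 60 and 72 = 6.
- Total for a woman who follows the full schedule: 1 + 6 = 7. One more is scheduled at early discontinuation if she stops early.
- Under criterion 4b the total is 0.

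**Step 4. Check that the row is read correctly.** From randomization, the fasting office visits are 10 to 16, 19, 22, 25 and 28. The telephone visits are 17, 18, 20, 21, 23, 24, 26 and 27, which is 8 and matches the number given in Section 4.1.1.2.3. All 7 numbered urine marks fall on office visits and none on telephone visits, so the row shows no sign of column shift.

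**Step 5. Serum test.** If Appendix 5 also governed screening, the Visit 1 serum test would bring the total to 7 + 1 = 8. A further serum mark appears at Visit 10, but its column position is uncertain and it is not counted.

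**The case against.** The best defence is that criterion 4b governs throughout. It names ligation expressly, it settles her status at entry, and no text reclassifies her at Visit 10. Appendix 5 concerns contraception and pregnancy reporting, orders no tests, and reaches its result only by leaving ligation off a list. That makes criterion 4b a plausible default for the SoA. It remains unstated, however, and Appendix 5 is the section headed as the definition of the very term the SoA uses.

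A second defence is that for-cause tests limit the gap: the SoA calls for them, and Appendix 2 allows additional tests at any time. This stands in part. Those tests are reactive or discretionary and supply no routine pre-dose result. Criterion 4b itself asks for a negative test before entry even from women aged 40 or older with at least a year without menses and raised FSH, yet asks for none from a premenopausal woman with a ligation.

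A reader might infer more than the documents support:
- *That the two texts also conflict on bilateral salpingectomy.* They do not. The criterion 4b list is introduced as inclusive, and such a woman is surgically sterilized under its wording too.
- *That screening is unsettled as well.* Appendix 2 refers it to Section 5.1.
- *That pregnant women will be dosed at some appreciable rate.* The documents give no rate of pregnancy after ligation. The contrast of 0 with 7 counts tests, not risk.
- *That the lists could be aligned in either direction if a sentence were added to test ligated women anyway.* Aligning to criterion 4b and then testing them would contradict the SoA limit to women of childbearing potential.

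**Conclusion.** The inconsistency holds and should be corrected. For a premenopausal woman with tubal ligation alone, the protocol supports either 0 or 7 scheduled urine pregnancy tests, one of the 7 before first dose, and does not say which.

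The conclusion rests on reading the Appendix 5 default rule together with its list, since Appendix 5 never states outright that a ligated woman is of childbearing potential. The number of women affected and the frequency of harm are unknown. Sample size, power and type I error are not touched. This is a drafting conflict with a safety consequence; it does not threaten the trial's efficacy conclusions.

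**What to change.** Use one definition, aligned to Appendix 5 as the more protective text. That preference is precautionary, because the documents contain no data on pregnancy after ligation.

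1. In criterion 4b, remove tubal ligation from the list of women not of childbearing potential and name bilateral salpingectomy for consistency. Adjust the description of women of childbearing potential so that ligation alone no longer takes a woman out of that group.
2. In the SoA, cite Appendix 5 in both pregnancy-test rows, so that women with ligation alone have the scheduled tests, including the one before first dose.
3. State how ligation counts toward the two-method contraception rule, which would otherwise newly apply to these women if sexually active. That choice is the sponsor's.

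The cost per affected woman is 7 local urine tests plus the Visit 1 serum test, 8 in all, with one more urine test if she discontinues early. The 8 tests fall at visits already scheduled, so no visits are added. The wording change is a protocol amendment and needs IRB/IEC approval under Section 10.1.1.
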